### **Exclusion Criteria**

- i. Have moderate-severe or severe aphasia.
- ii. Have impaired decision making capacity as determined by the U-ARE protocol for assessing capacity to provide informed consent (described in Section 9.0).

Every effort will be made to recruit a diverse population. Stroke in South Carolina occurs to men and women of all ethnic and racial groups. We have no criteria that should exclude any person based on race, gender, or ethnic category. Hence will anticipate that our sample will be diverse.

## **6.0 Number of Subjects**

N = 20

## **7.0 Setting**

Procedures will primarily be conducted virtually via telephone and/or telehealth using an MUSC approved electronic platform (e.g., Doxy.me video visit) or in-person in MUSC research space. When virtual, the subject will be located in their home or work environment and the research team member will be located in the College of Health Professions Research Building at [name] on the MUSC main campus or at an approved alternative work location.

## **8.0 Recruitment Methods**

Participants with stroke will be recruited from 2 sources:

- (1) The proposed research investigates stroke recovery; thus, it will be supported by the Clinical and Translation Tools and Resources (CTTR) Core of the NIH-funded Center of Biomedical Research Excellence (COBRE) in Stroke Recovery at MUSC. The CTTR Core facilitates subject recruitment through a bioinformatics-enabled database registry called RESTORE (all recruitment and database methods are approved under Pro#00037803). RESTORE currently contains contact information for ~1500 stroke survivors who have signed informed consent to be contacted for research participation and ongoing recruitment is expected to add 1-3 more subjects each week. The Co-I of this project ([name]) has successfully recruited >n=100 subjects for stroke rehabilitation studies using RESTORE in the past; thus, we are confident that recruitment goals for the present study will be met without difficulty.
- (2) In addition, potential subjects will be identified from the existing Stroke Telerehabilitation - Occupational Therapy (Tele-OT) Quality Improvement program that is actively treating patients (funded by the Duke Endowment). The proposed project will recruit stroke survivors from the existing Tele-OT program in the following way: patients who are

referred to Stroke Tele-OT are phoned (as per usual practice) by Telerehab therapists to schedule the first telerehabilitation screen or visit. Information about the current study will be provided to the tele-therapists who will then provide information to the patient during this initial phone call. If a potential participant expresses interest, a team member of the current study will contact the potential participant to answer questions and schedule their first study visit at which informed consent will be obtained prior to starting study procedures.

Digital and physical recruitment materials: To aid in recruitment, we will disseminate a flyer designed for this study. For potential participants identified via either of the above methods, we will send a templated recruitment email that contains a description of the study, a blank copy of the consent form for their review, and our study team's contact information.

## 9.0 Consent Process

[figure not shown]
Informed Consent will occur during the PRE visit after the aphasia eligibility screening. Informed Consent will be obtained by approved study personnel in one of two ways depending on a potential participant's preference: via telehealth (eConsent) or in-person on MUSC campus in research-designated space.

- **e-Consent:** A link to the REDCap eConsent will be provided to the participant via a hyperlink (text or email). An approved member of the study team will review the consent document over the phone or via videoconferencing with the participant. Ample time will be provided for the potential participant to ask questions. The participant will electronically sign the eConsent and submit the REDCap survey. The study team member will then electronically sign the eConsent and print a PDF of the document. The signed PDF will be emailed or mailed to participants for their records. A downloaded signed e-consent form will also be stored securely in a locked cabinet in a locked office. In addition, the signed e-consent will be maintained electronically on REDCap.
- **In-person:** The consent process will take place in a private room when the potential participant comes to the Stroke Recovery Research Center, which will occur at a scheduled time agreed upon between the study personnel and the participant. The content of the consent will be verbally explained to the participant and the participant will be asked if he/she has questions and/or concerns. If the person requests a waiting period, then one will be given. If the person desires to consent immediately, then the person will provide consent immediately. No study procedures will occur until the informed consent is obtained.

Capacity to Consent: We will assess each participant's capacity to provide informed consent using the Understanding, Appreciation, Reasoning, and Expression (U-ARE) protocol. The following procedures are in accordance with the U-ARE protocol's flowchart (See Figure 1). After reviewing the informed consent form, the trained study staff will perform the U-ARE interview to assess decisional capacity. This study will include individuals with aphasia (less than moderate/severe, per exclusion criterion i), which does not equate to an inability to provide informed consent. For individuals with aphasia, the U-ARE items will be presented with appropriate communication supports (described in "Aphasia Supports" in Section 10.0). If the participant's responses are satisfactory, then the study staff will obtain the participant's signature on the ICF. If the participant's responses are not satisfactory, then the study staff will contact the PI or a designated clinician Co-Investigator to conduct the decisional capacity assessment (as specified in Figure 1). If the clinician determines that the participant has the

capacity to consent, the clinician will obtain the signature from the participant. If the clinician determines that the participant does not have the capacity to consent, then the clinician will inform the participant that they are no longer eligible to participate in this study. The study staff will continuously monitor participants for potential changes in decision-making capacity throughout the duration of their participation in the study. The U-ARE protocol will be re-administered if any member of the study team suspects changes in a subject's decision-making capacity.

Figure 1.

## 10.0 Study Design / Methods

**Design:** This is a quasi-experimental, single group pilot study that investigates the impact of integrating cognitive rehabilitation into an 8-week OT-led activity- and participation-based stroke telerehabilitation program. Participants will attend a total of 15 study visits over 10 weeks. A summary and timeline of procedures are outlined and described in the following table.

**Visit Schedule:** To accommodate participant preference/comfort and feasibility, we have designed the visit schedule to be flexible in the following ways:

- The PRE assessment visit will occur within 1-10 days prior Telerehab session 1 and the POST assessment visit will occur within 1-10 days after Telerehab session 13.

- Given the 2–3-hour length of the PRE session, the participant and therapist may decide to split the PRE procedures over 2 visits if the participant becomes fatigued or has other time constraints.
- We will make an effort to schedule telerehab visits on the days and times of the participants' choosing to the extent that the therapists' schedules permit.
- In extenuating circumstances that lead to cancellations/missed sessions (e.g., serious weather event, illness, holidays):
  - Telerehab sessions may extend into an additional week. This would make the intervention duration 9 weeks instead of 8 and the duration of full participation 11 weeks instead of 10.
  - Make-up telerehab sessions may be added to any intervention week.

Week	Week 1	Weeks 2-3	Weeks 4-6	Weeks 7-9	Week 10
Session	PRE	1-4	5-10	11-13	POST
Mode (session duration)	Virtual (2-3 hrs)	Telerehab (45–75 min/session 2x/week)	Telerehab (45–75 min/ session 2x/week)	Telerehab (45–75 min/session 1x/week)	Virtual (2 hrs)
Study Procedures	
 
• Informed Consent
 
• Collect emergency contact information
 
• Administer characterization and outcome measures
 
• Complete fall risk stratification
 
• Telerehab Technology Training as needed
 
• Brief initial introduction to the intervention approaches: cognitive rehabilitation and cognitive orientation to occupational performance (CO-OP) therapy approach (described below)
 
	
 
• Cognitive Rehabilitation 2x/week for 2 weeks.
 
• At the end of the 4th session, develop a personalized, measurement-based home OT program (described below) for use in subsequent sessions
 
	Cognitive Rehabilitation + OT with CO-OP Approach 2x/week for 3 weeks	OT with CO-OP Approach 1x/week for 3 weeks.	Administer outcome measures

Sessions 1-4 will provide cognitive rehabilitation strategy training focused on attention and executive function.

Sessions 5-10 will review cognitive rehabilitation strategy training and focus on the application of cognitive skills while engaging in OT for performance of home- and community-based activities.

Sessions 11-13 will emphasize the application of cognitive skills while engaging in OT for participation in home- and community-based activities.

Aphasia Supports: To accommodate individuals with aphasia, we will use supportive communication strategies to facilitate comprehension and understanding, as recommended by the study speech language pathologist (SLP) and in line with best practices for this population. This may include using adaptive formatting (e.g., presenting small amounts of text at a time,

increasing spacing, using larger font), presented information verbally and/or visually, and allowing participants to respond verbally, in writing, or by pointing/selecting from a multiple-choice list.

## Session “PRE”: PRE-TREATMENT ASSESSMENTS

**Aphasia Screening:** Prior to consent, we will determine whether participants meet exclusion criterion *i* (moderate-severe or severe aphasia) by the following procedures:

1. The therapist will query whether the participant might have symptoms of aphasia: E.g., “Do you have any difficulty communicating with others since your stroke?”

If this question is endorsed or the therapist suspects aphasia based on their interactions, then:

2. The therapist will administer the Language Screening Test (LAST) form A. This 15-item measure tests expressive and receptive language. We will make adaptations to accommodate remote administration when needed. Participants will be excluded from the study if they score:
  - A. Less than 6/7 on the receptive index OR
  - B. Less than 4/8 on the expression index OR
  - C. A total score below 15/15 (but do not meet criteria A or B) and per clinical judgment:
    - For those meeting criterion C, the therapist conducting the assessment will consult with the study SLP to determine eligibility. If the therapist and SLP deem it necessary, the SLP will meet with the participant to do a more thorough evaluation of their aphasia and determine whether they should be included in the study.

**Sample Characteristics:** We will collect the following data at the initial visit that will be used to describe characteristics of the sample:

- Demographics: self-reported age, biological sex, gender, race, ethnicity, time since stroke, stroke location, pain, and stroke severity (NIH Stroke Scale).
- Technological Literacy via a questionnaire modified for stroke telerehabilitation
- The Occupational Therapy Occupational Profile to qualitatively document aspects of the participant’s context that impede/facilitate telerehabilitation including technology (internet, computer) and the physical and social home-context.
- We may also conduct medical chart review to collect the following information: stroke date, NIH Stroke Scale score, and discharge scores on stroke rehab assessments.

**Outcome Measures:** The research team member administering the outcome assessments will be trained on the administration and scoring of each assessment with standardized training videos, manuals, and appropriate supervision. We will assess cognition (objective and subjective), functional task performance, activity participation, and psychosocial function with the following measures administered at pre- and post-treatment unless otherwise specified:

Outcome Domain	Instrument
Cognition	MoCA
Cognition	NeuroQoL-Cognitive Function Short Form v.2.0
Functional Task Performance and Activity Participation	Patient Specific Functional Scale (PSFS)
Functional Task Performance and Activity Participation	Performance Quality Rating Scale (PQRS) a
Functional Task Performance and Activity Participation	Stroke Self Efficacy Questionnaire (SSEQ)
Psychosocial Function	Patient Health Questionnaire (PHQ-9) b
Psychosocial Function	Inventory of Psychosocial Functioning
Psychosocial Function	PROMIS Sleep Disturbance

aThe PQRS will not be administered at the PRE and POST visits and instead will be administered at actual telerehab visits to more proximally assess function. Specifically, it will be administered at the beginning of the first telerehab visit (session 1), the beginning of the first visit with OT (session 5), and at the end of the last telerehab visit (session 13).

bThe Columbia Suicide Severity Rating Scale (C-SSRS) will also be administered if suicidal ideation/intent is endorsed (as described in Section 12.0).

**Telerehab Technology Training:** Technology training and orientation will be provided as needed to participants to ensure understanding of the digital platform (Doxy.me). Study staff will provide written instructions via email, calendar invitation, or text message that include the webpage link to join the telerehab call with the therapist. Phone support may be provided as needed for clients who are unsuccessful with connecting at the scheduled appointment time. Study staff will orient the client to the video call interface and review how to turn the camera and microphone on and off to protect privacy, how to position themselves at the workspace in view of the camera to suitably participate in telerehab sessions, and how to contact the study staff or therapist if the video conference connection is lost.

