During a CO-OP task-practice session, the participant may be seated or standing at a table with the task objects arrayed within the reachable workspace. The therapist asks the client to identify the task goal (e.g., eating with a spoon), and the client is asked to explain how they plan to approach the activity using guided questions as needed (e.g., explaining movement strategies, set-up of the activity, key performance areas, etc.). The therapist intermittently provides verbal coaching and feedback such as “How do you think it is going?” and/or, “Can you tell me what is going well and what is not going well?” to guide the client through the selected task. Guided-questioning intervals will be adjusted according to patient success with the selected task, allowing the client time to problem-solve independently through errors depending on their level of understanding. Upon completion of the task, the therapist will ask the participant to “Check” their performance, asking questions such as, “How did you do?”, or “Is there anything you want to change the next time you try this task?”. The client will then engage in a discussion about his/her performance on the task according to the goals set prior to the start of the activity, (e.g., “I had trouble keeping my shoulder down while trying to bring the spoon to my mouth.”) The activity will be repeated as necessary to confirm understanding and integration of new strategies.

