### Session “POST”: POST-TREATMENT ASSESSMENTS

**Outcome Measures:** We will repeat the same measures administered at pre-treatment to assess cognition (objective and subjective), functional task performance, activity participation, and psychosocial function:

Outcome Domain	Instrument
Cognition	MoCA
Cognition	NeuroQoL-Cognitive Function Short Form v.2.0
Functional Task Performance and Activity Participation	Patient Specific Functional Scale (PSFS)
Functional Task Performance and Activity Participation	Performance Quality Rating Scale (PQRS) a
Functional Task Performance and Activity Participation	Stroke Self Efficacy Questionnaire (SSEQ)
Psychosocial Function	Patient Health Questionnaire (PHQ-9) b
Psychosocial Function	Inventory of Psychosocial Functioning
Psychosocial Function	PROMIS Sleep Disturbance

aThe PQRS will not be administered at the PRE and POST visits and instead will be administered at actual telerehab visits to more proximally assess function. Specifically, it will be administered at the beginning of the first telerehab visit (session 1), the beginning of the first visit with OT (session 5), and at the end of the last telerehab visit (session 13).

bThe Columbia Suicide Severity Rating Scale (C-SSRS) will also be administered if suicidal ideation/intent is endorsed (as described in Section 12.0).

**Telerehab Experience Survey:** At the POST visit, participants will complete two brief surveys regarding their experiences of completing the telerehabilitation program, the Acceptability of Intervention Measure (AIM) and the Intervention Appropriateness Measure (IAM). They will also have the option to provide narrative, qualitative responses about what they liked and did not like about the program. The survey will be administered via Redcap.

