### **14.0 Risks to Subjects**

There is a minor risk of mental and/or physical fatigue from engaging in the cognitive rehabilitation and occupational therapy rehabilitation intervention. There is also a risk of falling during the occupational therapy sessions. There is a risk that stroke survivors may experience sadness, fear, or anger if they have difficulty with the assessments or intervention because they may develop a greater realization of their deficits. It is also possible that the task-practice sessions result in temporary muscle soreness or fatigue. These risks to participants are no more than a usual-care stroke rehabilitation assessment and/or intervention session.

There is a risk of a loss of confidentiality of personal information that is used in this study although researchers will take appropriate steps to protect any information collected about the participants.

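### The PQRS is rated before therapy at sessions 1 and 5 but after therapy at session 13, so its change score includes any transient same-session effect, of unknown size and sign.

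*Combined protocol and SAP*

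**What the plan says.** Footnote a to the outcome table in Section 10.0 (Session PRE) sets three PQRS occasions. For the first, "it will be administered at the beginning of the first telerehab visit (session 1"; the other two fall at "the beginning of the first visit with OT (session 5), and at the end of the last telerehab visit (session 13". The same footnote stands under the Session POST table, where it begins "The PQRS will not be administered at the PRE and POST visits and instead will be administered at actual telerehab visits". The reason offered is that function is assessed closer to the therapy itself. No reason is given for moving from the start of a session to the end.

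On session 13, Section 10.0 states: "Sessions 11-13 will emphasize the application of cognitive skills while engaging in OT for participation in home- and community-based activities". Its visit table lists these weeks as "Telerehab (45–75 min/session 1x/week"; Section 3.0 gives about 45 to 60 minutes. Both are total session lengths. In the account of a CO-OP task-practice session, "The therapist intermittently provides verbal coaching and feedback", and "The activity will be repeated as necessary to confirm understanding and integration of new strategies". Section 14.0 adds: "It is also possible that the task-practice sessions result in temporary muscle soreness or fatigue".

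Section 4.0 defines the PQRS as a 0-10 ordinal rating made by the OT over the video call, on a task that is not among those picked for the PSFS. Section 11.0 evaluates change from pre- to post-treatment in each outcome. It does not say whether session 1 or session 5 is the PQRS baseline, and it makes no allowance for where in a session a rating falls.

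**The concern.** A change score is interpretable when both ratings are taken under the same conditions. Here the early ratings are made before any of that day's therapy and the final one after a complete session. A participant who has just been coached and has warmed up may perform better than at the start of the same session. A tired participant may perform worse. Either effect would be counted as change over the program.

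The design cannot correct for this. There is one group, so no concurrent control carries the same same-session effect and allows it to be subtracted. A larger sample would narrow the interval but leave the shift in place.

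The PQRS matters because, of the three instruments in the functional performance and participation domain, it is the only one rated by an observer; the PSFS and SSEQ are patient-reported. The stated aim (Section 1.0) is to produce effect estimates that inform larger trials, so a shifted estimate would carry forward into their planning.

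**Working it through.** The documents give no SD, effect size or within-session shift for the PQRS, so there is no plan figure to reproduce. The check has two parts.

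**Timing, from the text**

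| PQRS occasion | Point in session | Therapy already given that day |
|---|---|---|
| Session 1 | beginning | none |
| Session 5 | beginning | none |
| Session 13 | end | the full session |

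The asymmetry is the same whichever early rating is the baseline.

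Let G12 be the true gain up to the start of session 13, g13 the gain from session 13 that does not fade at once, and δ the transient same-session shift.

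- Expected change as scheduled: G12 + g13 + δ.
- Expected change with the final rating at the beginning of session 13: G12.

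A single end-of-session rating cannot separate g13 from δ.

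**Size, under assumptions**

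- n = 20 (Section 6.0).
- δ between 0 and 1.0 point in either direction: assumed.
- SD of change between 1.5 and 3.0 points: assumed.
- δ is treated as the same for every participant.

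Distortion in SD units = δ / SD.

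95% confidence interval half-width for a mean change, in SD units = t(0.975, 19) / √20 = 2.093 / 4.472 = 0.468.

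| SD of change | δ = 0 | δ = 0.5 | δ = 1.0 | Half-width in points (0.468 × SD) |
|---|---|---|---|---|
| 1.5 | 0 | 0.33 | 0.67 | 0.70 |
| 2.0 | 0 | 0.25 | 0.50 | 0.94 |
| 2.5 | 0 | 0.20 | 0.40 | 1.17 |
| 3.0 | 0 | 0.17 | 0.33 | 1.40 |

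Negative δ gives the same sizes with the sign reversed. A 1.0-point shift exceeds the half-width when the SD is below 1.0 / 0.468 = 2.14 points. A 0.5-point shift does not exceed it anywhere in this range.

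The plan specifies no significance test. As a further illustration only, take a two-sided 5% paired t-test with n = 20 and no true change (noncentral t, noncentrality (δ/SD) × √20). It would reject with these probabilities:

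| SD of change | δ = 0.5 | δ = 1.0 |
|---|---|---|
| 1.5 | 29% | 81% |
| 2.0 | 19% | 57% |
| 2.5 | 14% | 40% |
| 3.0 | 11% | 29% |

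With δ = 0 the rate is the nominal 5%.

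**The case against.** The schedule can be defended. A rating before any therapy and another after all of it bracket the full 13 sessions, and placing them at therapy visits follows the footnote's stated purpose. That purpose, however, explains the use of therapy visits and not the switch within the session; a rating at the start of session 13 serves it equally well.

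The strongest substantive point is that the rated task is one not picked for the PSFS. The coached repetition in the CO-OP description concerns the task selected for that session, so direct rehearsal of the PQRS task may be limited. This stands as a reason to expect a smaller shift. It does not remove the problem: no section keeps the rated task out of session 13 or out of the home program, and general warm-up, recent coaching and fatigue do not depend on rehearsing the same task.

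Size is also fairly disputed. Warm-up and fatigue could offset each other, and Section 14.0 describes the fatigue risk as minor or merely possible. A net effect near zero fits the documents as well as a large one.

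A reader might infer more than the text supports in four ways:

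- That the final rating follows at least 45 minutes of coached practice. The stated minutes are whole-session length, which also covers the emergency-information check and the planning and review discussion; coaching is described as intermittent, and no practice time is given.
- That the PQRS fails to measure lasting change. Section 11.0 defines post-treatment as directly after the intervention, and the protocol claims retention for no outcome.
- That the comparison with the 30 historical patients is distorted too. Section 11.0 refers only to participation measures. It does not say that the historical data include the PQRS, or when it would have been rated.
- That the change is inflated. The direction cannot be determined from the documents.

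**Conclusion.** The point holds as a timing asymmetry, written identically in both places where the PQRS schedule appears. By construction the PQRS change includes any transient effect of session 13 that the earlier ratings lack, and neither the design nor the analysis can remove it.

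Its size and sign are unknown. The range of 0 to about 0.67 SD, set against a half-width of about 0.47 SD, rests wholly on the assumed shifts and SDs; the existence of the asymmetry does not. The consequence is limited: one of eight outcome instruments, none named as primary, in a pilot of 20 that produces preliminary effect sizes. It merits correction because the change is small and because a start-of-session rating that was never taken cannot be recovered later.

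**What to change.** In footnote a under both outcome tables (Session PRE and Session POST), set the final analysed PQRS at the beginning of session 13, the same within-session point as the ratings at sessions 1 and 5. The end-of-session-13 rating may be kept as descriptive. The difference between the two session-13 ratings would then show how large the combined same-day change was. Make the change before further participants reach session 13.

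Cost: one line in two footnotes. The analysed rating omits the contribution of the last of 13 sessions. If both ratings are taken, session 13 is a few minutes longer. Moving the final PQRS to the POST visit is less suitable, because it would reverse the protocol's stated choice to rate at therapy visits.
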